7. STATISTICAL METHODS

7.1. Randomization and Stratification

The randomization ratio for Part 1 of the study will be 1:1 for active (pexidartinib) versus placebo. Randomization will be stratified by US versus non-US sites and by upper extremity versus lower extremity involvement.

7.2. Analysis Sets

Randomized Analysis Set

The Randomized Analysis Set consists of all subjects in this study that were randomized.

ITT Analysis Set

The Intent-to-treat (ITT) Analysis Set is defined as all randomized subjects, which is the same as the Randomized Analysis Set. The primary efficacy analysis as well as all other efficacy analyses will be performed in the ITT Analysis Set. Subjects will be included in the treatment group to which they were randomized, regardless of the treatment actually received.

Safety Analysis Set

The Safety Analysis Set consists of all subjects in the Randomized Analysis Set who received at least one dose of study treatment. All safety analyses will be completed in the Safety Analysis Set. Subjects will be included in the treatment group based on the actual treatment they received.

Per-protocol Analysis Set

The Per-protocol Analysis Set will be defined as subjects in the ITT Analysis Set who did not have major eligibility/protocol violations and who are compliant with regard to study treatment administration, defined as taking at least 70% of their scheduled dose of study treatment, regardless of scheduled dose reduction.

7.3. Procedures for Handling Missing, Unused, and Spurious Data

For the primary efficacy analysis as well as for all analyses of responder proportion endpoints performed on the ITT and Per-protocol Analysis Sets, subjects who do not provide data for the responder endpoint will be considered nonresponders, ie, assigned to the less favorable outcome for the endpoint. Subjects who discontinue the study before Week 25 and do not have a Week 25 MRI will be considered nonresponders. Analysis of the endpoints involving range of motion and PROs, which are measured at multiple time points, by comparing the central tendency of continuous variables between treatment groups (not the responder type of analysis for a binary variable), will be performed using mixed models for repeated measurements (MMRM) incorporating all available measurements from each subject.^{24,25,26,27,28}

7.4. General Statistical Considerations

Continuous variables will be summarized by the number of observations, mean, standard deviation, median, 25th and 75th percentile, and minimum and maximum values. Categorical variables will be summarized using frequency counts and percentages.

In general, the baseline value for an efficacy variable, including that for a PRO variable, is the last non-missing value before randomization. The baseline value for a safety variable is the last non-missing value before the first dose of study treatment. The exceptions are several special variables in Part 2, such as the tumor response and duration of response variables evaluated for pexidartinib treatment for subjects randomized to placebo in Part 1; in such cases, the baseline for Part 2 is defined as the last non-missing value before the first dose in Part 2. Further details are contained in the following sections and in the Statistical Analysis Plan (SAP).

For the primary efficacy endpoint and secondary efficacy endpoints with the exception of duration of response, treatment comparison at Week 25 will be performed based on the data collected during the visits between baseline and Week 25. Point estimate and accompanying 95% confidence interval (CI) will be computed. For duration of response, Kaplan-Meier product limit methodology will be utilized to provide estimates, including those for the median and 25th and 75th percentiles.

All statistical tests will be 2-sided. Unless otherwise specified, all tests will be carried out at the alpha = 0.05 level of significance.

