Study Duration	
Each subject will spend a maximum of 6 weeks in screening. Part 1 will be a maximum of 24 weeks in duration. Patients for whom disease progression is confirmed at or after Week 13 but before Week 25 (by independent central radiological evaluation) and are taking placebo are eligible for entry into Part 2 early prior to 30 Sep 2016. The duration of Part 2 will vary among subjects, as this portion of the trial will continue until all subjects in this phase have either completed at least the Week 49 Visit or withdrawn from the study. The study will end with the last subject last visit. Subjects who complete Part 2 will be eligible to continue for longer efficacy and safety follow-up or to enter a separate protocol to continue receiving pexidartinib until disease progression, unacceptable toxicity, or the occurrence of other termination criteria.

Study Sites & Locations	
Approximately 45 study sites internationally across the US, Canada, EU, and Australia.

Planned Sample Size	
Approximately 126 subjects across sites globally are planned.

Test Product, Dose, and Route of Administration	
The study treatment, either pexidartinib or placebo, will be administered orally daily in capsule form. Each capsule of pexidartinib will contain 200 mg of PLX3397 (J-3397-AF in hydroxypropyl methylcellulose capsules) or matching placebo. In Part 1, subjects will take five capsules a day (1000 mg/d pexidartinib or matching placebo) divided into a morning dose of two capsules and an evening dose of three capsules. After 2 weeks (P1-C1D15), dosing will be reduced to two capsules in the morning and two capsules in the evening (800 mg/d pexidartinib or matching placebo). All subjects will begin Part 2 by continuing to take the same number of capsules per day of open-label 800 mg/d pexidartinib. Doses will be taken in the fasting state (no food for 1 hour before and 2 hours after dosing, with a low-fat snack if needed) at approximately the same times of the day and approximately 12 hours apart. Each treatment cycle is 28 days.

	
The study treatment for home administration during Part 1 will be dispensed to the subject for the first time at the Cycle 1, Day 1 visit of Part 1, and the study treatment for home administration during Part 2 will be dispensed to the subject for the first time at the Cycle 1, Day 1 visit of Part 2.

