3. STUDY DESIGN

3.1. Overall Plan

[figure not shown]
This trial is a two-part multi-center Phase 3 study in subjects with symptomatic PVNS or GCT-TS for whom surgical resection would be associated with potentially worsening functional limitation or severe morbidity (locally advanced disease). In Part 1, the double-blind phase, eligible candidates will be centrally randomized in a 1:1 ratio to receive either pexidartinib or placebo for 24 weeks. Randomization will be stratified by US versus non-US sites and by upper extremity versus lower extremity involvement.

Study treatment will be administered twice a day, every day. For the first 2 weeks in Part 1, subjects will take two capsules in the morning and three capsules in the evening, 1000 mg/d pexidartinib or matching placebo. Thereafter, dosing will be reduced to two capsules in the morning and two capsules in the evening, 800 mg/d pexidartinib or matching placebo. Subjects who had a dose reduction during the first 2 weeks will continue treatment at their reduced dose. Each treatment cycle will be 28 days in duration and subjects will be treated for up to 6 Cycles. Dose reductions, interruptions, and re-escalations after previous reductions for toxicity are permitted according to pre-specified guidelines. Those subjects who complete Part 1 (ie, complete 24 weeks of dosing and the Week 25 assessments) will be eligible to advance to Part 2, a long-term treatment phase where all subjects will take up to four capsules per day (800 mg/d) of open-label pexidartinib. Effective 30 Sep 2016, subjects on placebo are no longer allowed into Part 2 to receive open-label pexidartinib.

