MRIs will be performed at Week 13 (Cycle 4, Day 1 visit of Part 1 [P1-C4D1]) and Week 25. If disease progression is indicated clinically or by local radiologic assessment according to RECIST 1.1 at or after Week 13 but before Week 25, the Investigator may request a central review for evaluation of disease progression. Any disease progression before Week 25 must be verified by a central MRI reading. If a central reading confirms RECIST 1.1-defined disease progression, treatment assignment will be unblinded, and subjects receiving placebo will be eligible for early entry into Part 2 of the study. Effective 30 Sep 2016, subjects receiving placebo will be discontinued instead of being eligible to enter Part 2. Subjects receiving pexidartinib will be discontinued from the study unless the Investigator and the Sponsor's Medical Monitor judge that the subject would potentially benefit from continued treatment with pexidartinib. For those subjects who undergo surgical resection after Week 25, an MRI will be performed 4 months after surgery.

Part 2 will continue until all subjects have either reached at least the Week 49 visit, ie, an additional 24 weeks of study treatment beyond the placebo-controlled phase, or withdrawn from the trial (Figure 3.1). As in Part 1, dose reductions, interruptions, and re-escalations after previous reductions for toxicity are permitted according to pre-specified guidelines. Subjects who complete Part 2 will be eligible to continue pexidartinib treatment for study of longer efficacy and safety follow-up assessed per the schedule in Part 2 or to enter a separate protocol to continue receiving pexidartinib.

Figure 3.1: Study Schematic*

* Effective 30 Sep 2016, subjects on placebo are no longer allowed into Part 2 to receive open-label pexidartinib.

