For Group A, tumor assessment data from both Part 1 and Part 2 will be combined, and the baseline assessment will be the one recorded at the Screening visit. For Group B, the duration of response will be censored at Week 25 visit if no disease progression was documented, with the screening assessment serving as baseline. For Group C, the tumor assessment data in Part 2 will be used, with the baseline assessment being the last one before the first dose of pexidartinib in Part 2.

For each of the above three groups, the percentage and 95% CI will be provided for the best overall response in the order of CR, PR, SD, PD, and “Inevaluable.”

The analyses for the primary efficacy endpoint and BPI Worst Pain NRS item associated endpoints will also be performed on the Per-protocol Analysis Set as a sensitivity analysis.

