7.10.1. Analysis of Treatment-emergent Adverse Events

TEAEs are AEs that occur, having been absent before the first dose of study treatment, or have worsened in severity after the initiating the study treatment. TEAEs will be coded using MedDRA and assigned grades based on version 4.0 of the National Cancer Institute's Common Terminology Criteria for Adverse Events (NCI CTCAE). The number and percentage of subjects reporting TEAEs will be tabulated by the worst CTCAE grade, SOC, and PT, with a breakdown by data set (Section 7.10). Similarly, the number and percentage of subjects reporting treatment-emergent SAEs will be tabulated, as well as TEAEs leading to discontinuation of study treatments.

A by-subject AE (including treatment-emergent) data listing including but not limited to verbatim term, preferred term, system organ class, CTCAE grade, and relationship to study treatment will be provided. Deaths, other SAEs, and other significant AEs, including those leading to discontinuation of study treatments, will be listed.

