7.10.2. Clinical Laboratory Evaluation Analyses

Descriptive statistics will be provided for the clinical laboratory results by scheduled time of evaluation and by treatment group and study part for the Safety Analysis Set, as well as for the change from baseline. The baseline value is defined as the last non-missing value before the initial administration of study treatment. In addition, mean change from baseline will be summarized for the maximum and minimum post-treatment values and the values at the End of Treatment visit.

Abnormal clinical laboratory results will be graded according to NCI CTCAE version 4.0, if applicable, and the grade will be presented in a by-subject data listing. A shift table, presenting by treatment group the 2-way frequency tabulation for baseline and the worst post-treatment value according to the NCI CTCAE grade, will be provided for clinical laboratory tests. Abnormal clinical laboratory test results deemed of clinical significance or of Grade 3 or 4 will be listed.

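### For placebo subjects who crossed over to pexidartinib, the safety baseline and TEAE reference precede placebo, nominally 84 to 168 days before the first pexidartinib dose

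*Combined protocol and SAP*

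**What the plan says.** The general rule for safety variables is in Section 7.4: "The baseline value for a safety variable is the last non-missing value before the first dose of study treatment". The Synopsis entry on the test product fixes the meaning of the term: "The study treatment, either pexidartinib or placebo, will be administered orally daily in capsule form".

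The safety sections repeat the rule. Section 7.10.2 (laboratory) says "The baseline value is defined as the last non-missing value before the initial administration of study treatment", and Sections 7.10.3 (vital signs) and 7.10.4 (ECG) use the same sentence. Section 7.10.5 (ejection fraction) gives no baseline of its own, so Section 7.4 applies. Section 7.10.1 defines TEAEs as events "having been absent before the first dose of study treatment, or have worsened in severity after the initiating the study treatment".

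Section 7.4 also allows a different baseline in Part 2 for some variables: "The exceptions are several special variables in Part 2, such as the tumor response and duration of response variables". Section 7.6.2 applies this to Group C, the former placebo subjects in Part 2, "with the baseline assessment being the last one before the first dose of pexidartinib in Part 2".

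Crossover was possible for a limited time. Placebo subjects could enter Part 2 at Week 25, or earlier if progression was centrally confirmed "at or after Week 13 but before Week 25". Section 3.1 then closes this route: "Effective 30 Sep 2016, subjects on placebo are no longer allowed into Part 2 to receive open-label pexidartinib". Part 2 data from those who had already crossed over stay in the analysis. Section 7.10 places them in TEAE data set (iii), all open-label data, and data set (iv), the aggregate pexidartinib data.

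**The concern.** For a crossover subject, Part 2 is the first exposure to pexidartinib. The natural reference for on-drug safety is the state just before that exposure. The stated rule uses the state before placebo instead, so a Part 2 change from baseline combines whatever happened on placebo with whatever happened on pexidartinib. The plan already avoids this for tumor response in the same subjects.

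The early weeks of exposure matter most for this drug. Section 1.5 describes transaminase rises in the first cycle, and the December 2017 hepatic safety update places cholestasis cases in the first 8 weeks. For crossovers those weeks fall in Part 2. At stake is how cleanly the descriptive open-label safety tables attribute change to pexidartinib.

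**Working it through.** The plan gives no figure on this point beyond its calendar, which reproduces: 6 cycles × 28 days = 168 days = 24 weeks to the Week 25 visit, and 3 cycles × 28 days = 84 days = 12 weeks to the Week 13 visit (P1-C4D1).

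**Age of the baseline at the first pexidartinib dose.** The gap is the day of first pexidartinib minus the day of the baseline value, with P1-C1D1 as day 0.

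| Variable | Baseline under the stated rule | Week 13 entry | Week 25 entry |
|---|---|---|---|
| Vital signs, ECG | P1-C1D1, pre-dose (Section 15.2.3) | 84 | 168 |
| Laboratory | P1-C1D1, or up to 72 h earlier (Section 15.2.3) | 84 to 84 + 3 = 87 | 168 to 168 + 3 = 171 |
| Ejection fraction | Screening scan, Day -42 to -1 (Section 15.2.1) | 84 + 1 = 85 to 84 + 42 = 126 | 168 + 1 = 169 to 168 + 42 = 210 |

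These are nominal days. A 7-day visit window widens the range for vital signs and ECG to 84 − 7 = 77 and 168 + 7 = 175 days.

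**What enters the summaries.** Let B0 be the pre-placebo value, B1 the last value before pexidartinib, and V a Part 2 value. The plan reports

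V − B0 = (V − B1) + (B1 − B0).

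The second term is change on placebo, and its sign can be either.

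- *Laboratory shift table (Section 7.10.2).* The baseline grade is taken at B0 and the worst grade over all post-treatment values. No study-part split is stated, so a crossover's worst value may come from either period.
- *QTcF maximum change (Section 7.10.4).* The maximum runs over all post-treatment evaluations, with the same consequence. Section 7.2 groups subjects by the treatment actually received, which for a crossover is both.
- *TEAE status in sets (iii) and (iv).* Take an event present before placebo that resolves and returns on pexidartinib at no worse severity. It was not absent before the first dose of study treatment and has not worsened, so it is not treatment-emergent. In the other direction, an event that begins on placebo and continues unchanged is treatment-emergent, and the plan does not say whether it is carried into sets (iii) and (iv).

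**What a reset would achieve at Week 25.** Section 15.3.1 schedules laboratory tests and vital signs ahead of the P2-C1D1 dose (gap 0 days) and the ejection-fraction scan within the preceding 7 days (gap at most 7). For ECG the gap is near 0 if a pre-dose Week 25 tracing exists. If it does not, the last scheduled Part 1 tracing is P1-C1D15, 14 days after first dose. The gap is then 168 − 14 = 154 days, a gain of only 14. For Week 13 entry, that same tracing is 84 − 14 = 70 days old.

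**The case against.** The strongest objection is that Section 7.4 leaves its exception list open and refers details to the sections that follow and to the SAP. A Part 2 safety baseline is just what a SAP might contain, and its separate text was not available here. This stands as a limit: one can say only that no protocol section resets the safety baseline. It does not remove the point, because the sections that follow restate the unreset rule. A SAP that resets it would contradict Sections 7.10.2 to 7.10.4 and would need aligning with them.

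Second, many safety outputs do not depend on this baseline. Absolute QTc categories and CTCAE grade listings are not changes from baseline, and the liver criteria in Table 5.1 and Section 9.3.1 are multiples of ULN. By-visit ECG and ejection-fraction summaries already separate the parts, because visits carry part labels, and Sections 7.10.2 and 7.10.3 split the main laboratory and vital-sign statistics by study part. All of this stands and narrows the scope. Separating Part 2 values does not, however, change the value they are compared with.

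Third, the recurring-event example is narrow, the affected group is closed, and days between visits are not a measure of bias. Early entry also needs an expedited central read and sponsor authorisation, so 84 days is a nominal minimum. These points stand too.

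A reader might infer that pooled pexidartinib TEAE rates are understated. The documents do not support a direction: a reset would add some recurrences and might remove events ongoing unchanged from placebo. A reader might also infer that data set (iv) is meant to exclude subjects who took pexidartinib only in Part 1, since its wording names those who received it in Parts 1 and 2. Its label as aggregate data shows that inclusion was intended, and those subjects' events remain in set (i). This is a wording defect only.

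**Conclusion.** The point holds within limits. As written, the protocol measures crossovers' on-pexidartinib safety from a value taken before placebo: nominally 84 to 168 days before the first pexidartinib dose, up to 171 for laboratory tests and up to 210 for ejection fraction. It resets the tumor baseline for the same subjects.

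The affected outputs are descriptive and concern crossovers only: Part 2 change from baseline, baseline grade and worst value in the laboratory shift table, QTcF maximum change, and TEAE status in sets (iii) and (iv). A reader might suppose that the blinded safety comparison is compromised. It is not, because sets (i) and (ii) use Part 1 data, where the pre-treatment baseline is the right one for both arms.

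The number of crossovers is not given, so neither the size nor the direction of any effect on rates or means can be computed. The conclusion assumes nominal visit timing and that the separate SAP does not already reset the safety baseline. The correction is worth making because it is cheap and most of the values it needs are already scheduled.

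**What to change.** For placebo subjects who entered Part 2:

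- Define the baseline for Part 2 laboratory, vital-sign, ECG and ejection-fraction summaries as the last value before the first pexidartinib dose.
- Use the subject's state at that point as the TEAE reference in sets (iii) and (iv), and state how events ongoing from placebo are handled.
- Split the laboratory shift table and the QTcF maximum change by study part.
- Where no pre-dose Week 25 ECG exists, use the last Part 1 ECG and report it as such.

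Two scheduling conflicts must be reconciled alongside this:

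- *Week 25 ECG.* Table 15.3 note a treats most Week 25 procedures as already done at the Completion visit, which includes an ECG. Section 15.2.16 and Table 15.2 note c instead send continuing subjects to the P2-C1D1 schedule, where Section 15.3.1 and Table 15.3 note g list only a post-dose ECG.
- *Week 25 ejection fraction.* Section 15.3.1 schedules a scan 168 − 84 = 84 days after the Week 13 visit. Section 6.4.6 restricts repeats to intervals of more than 3 months (about 91 days).

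As a minor wording change, define set (iv) as all subjects with at least one pexidartinib dose in Part 1 or Part 2, with data from the first pexidartinib dose.

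The cost is a few sentences in the SAP, matching edits to Sections 7.4 and 7.10, and a small amount of programming. TEAE counts may move in either direction. The ECG gain may be slight where no pre-dose Week 25 tracing was taken.

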7.5. Study Population Data

Subject disposition will be summarized for each randomized treatment group and in total for the ITT Analysis Set. The total number of subjects for each defined analysis population will also be tabulated. The demographic and baseline characteristics will be summarized descriptively for the ITT, Per-protocol, and Safety Analysis Sets. Study treatment exposure and study duration will be summarized using descriptive statistics by treatment group for the Safety Analysis Set.

7.6. Efficacy Analyses

7.6.1. Primary Efficacy Analysis

The primary efficacy endpoint is the proportion of subjects who achieve a CR or PR at the Week 25 Visit (Table 2.1) based on centrally read MRI scans and RECIST 1.1. The primary analysis will be completed using the ITT Analysis Set. The proportions in the two treatment groups will be compared using Fisher's exact test (two-sided) at the alpha = 0.05 level of significance. In addition, the two-sided 95% CI for the difference between the responder proportions in the two treatment groups will be provided, using the Wilson method.^{29,30}

As a supportive analysis, mid-p adjustment of Fisher's exact test will also be performed.^{31,32}

Additionally, as a sensitivity analysis, the Cochran-Mantel-Haenszel test will also be carried out with the strata of US and non-US sites.

